13.4 Reporting and Exclusions

13.4.1 Evaluation of Toxicity

All participants will be evaluable for toxicity from the time of their first dose of study medication.

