4. REGISTRATION PROCEDURES

4.1 General Guidelines for DF/HCC Institutions

Institutions will register eligible participants in the Clinical Trials Management System (CTMS) OnCore. Registrations must occur prior to the initiation of protocol therapy. Any participant not registered to the protocol before protocol therapy begins will be considered ineligible and registration will be denied.

An investigator will confirm eligibility criteria and a member of the study team will complete the protocol-specific eligibility checklist.

Following registration, participants may begin protocol therapy. Issues that would cause treatment delays should be discussed with the Overall Principal Investigator (PI). If a participant does not receive protocol therapy following registration, the participant's registration on the study must be canceled. Registration cancellations must be made in OnCore as soon as possible.

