7.5 Time Period for Collection of Adverse Events

Adverse events will be collected from the time treatment, , throughout the treatment period and including the follow-up period of 30 days after the last dose of durvalumab and tremelimumab, or at the start of a new treatment

Serious adverse events will be recorded from the time treatment through30 days after the last dose of durvalumab and tremelimumab or the start of new treatment.

7.6 **Post-Study Events**

After the subject has been permanently withdrawn from the study, there is no obligation for the investigator to actively report information on new AEs or SAEs occurring in former study subjects after the 90-day safety follow-up period. However, if an investigator learns of any SAEs, including death, at any time after the subject has been permanently withdrawn from study, and he/she considers there is a reasonable possibility that the event is related to the investigator and product, the investigator should notify the Overall PI and AstraZeneca or its

representative.

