7.10 Expedited Adverse Event Reporting

7.10.1 Investigators **must** report to the Overall PI any serious adverse event (SAE) that occurs after informed consent, during treatment, or within 90 days of the last dose of treatment on the local institutional SAE form.

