9.1.2 Fresh Tumor Biopsies

Mandatory pre- and on-treatment fresh tumor biopsies will be obtained from patients enrolling to the trial. In the event the biopsy is not clinically feasible in the opinion of the treating investigator or interventionalist performing the procedure, exceptions to one or both fresh biopsy requirements are possible after discussion with the principal investigator.

The pre-treatment biopsy should be obtained following consent and prior to the first dose of any study medication (prior to Cycle 1 Day 1). The on-treatment biopsy may be obtained anytime between Cycle 2 Day 1 (after completion of the study medication infusions) to Cycle 2 Day 8.

An additional optional biopsy at the time of disease progression will also be offered to patients if deemed clinically feasible by the treating investigator. In patients undergoing re-treatment with tremelimumab, the time of progression biopsy may be obtained either prior to the initiation of re-treatment or upon progression following re-treatment. Preferably, time of progression biopsies should be obtained prior to the initiation of another cancer treatment. However, in the event that it is not possible to perform the biopsy before another treatment is begun, the biopsy can be obtained up to 60 days after the last dose of study medication.

Pre- and on-treatment core biopsy samples a minimum of 2 cores should be collected, if clinically feasible. A 16-18 gauge needle are preferable, but a 20 gauge core needle biopsy is also acceptable. For more information, please refer to the Thoracic Oncology Program 16-549 Biopsy Collection Guidelines. In the event that not enough tissue is obtained, priority should go to immune profiling.

If a core biopsy is judged to be too unsafe or difficult for the participant in the opinion of the treating investigator, a fine needle aspirate (FNA) or cytology sample can also be collected. The goal for a thoracentesis or paracentesis procedure will be 500 - 1000 mL collected in a standard collection tube. The goal for an FNA will be three distinct passes. Less than the goal amount of tissue is acceptable for any of the biopsy collection methods, and should be based upon the clinical judgment of the treating investigator and the clinician performing the procedure.

All tumor biopsy samples should be labeled with the protocol number, study subject number, date of collection, and identified as either "pre-treatment," "on-treatment," or "time of progression."

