13.3 Analysis of Primary and Secondary Endpoints

The primary and secondary analyses will include all eligible patients who started assigned therapy. The exception to this includes the planned analysis of toxicity data, which will include all patients who received study drug regardless of eligibility. Response will be assessed using the modified RECIST criteria for mesothelioma; toxicity will be graded using CTCAE v. 4.03.

For the analysis of the response efficacy measures, participants will be censored if they are alive and without disease progression at the date of the last disease evaluation. In the case of OS, participants will be censored if they are living at the date last known alive.

Time-to-event data, such as PFS and OS, will be estimated using the Kaplan-Meier method, and Cox proportional hazards models will be used to estimate hazard ratios. Comparisons of groups will be made using the logrank test and Cox modeling.

Categorical data, such as response rates (CR+PR) and toxicity, will be compared using Fisher's exact tests with a one-sided type I error rate of 10%; multivariable logistic regression modeling will be used to adjust for the effect of any covariates that are associated with these categorical outcomes. Though none are currently planned, any continuous outcomes will be analyzed using Wilcoxon rank sum test, and multivariable linear regression models may be used to adjust for multiple associations with outcome.

Modeling procedures will implement backward selection; variables significant at the 0.10 level in the univariate setting will be chosen for inclusion in an initial full model, and at each step the least significant variable will be removed from the model. Only those covariates with p<0.05 will remain in any final models, unless there are factors identified by the study team as crucial to model interpretation.

Point estimates of all endpoints will be accompanied by the corresponding two-sided 80% confidence intervals. The method of Atkinson and Brown will be used for the estimation of the confidence interval for response.

In the event that there are missing data, no imputation of the missing data will be conducted. We will assume that data are missing at random and will conduct all analyses as originally planned because we do not anticipate an excess of missing data.

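### Sections 7.8 and 7.10.1 disagree on when SAE reporting starts, and complications of the mandatory pre-dose research biopsy fall in that interval and in no planned safety analysis

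*Combined protocol and SAP*

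**What the plan says.** **The procedure.** Section 9.1.2 states: "Mandatory pre- and on-treatment fresh tumor biopsies will be obtained from patients enrolling to the trial". On timing it says: "The pre-treatment biopsy should be obtained following consent and prior to the first dose of any study medication". Exceptions to one or both biopsies are possible after discussion with the principal investigator, and a fine needle aspirate or cytology sample may replace a core biopsy. Willingness to undergo the biopsy is an eligibility criterion (3.1.5). The tissue serves the exploratory objectives (1.4, 2.6.1).

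**Collection and reporting.** Section 7.8 has investigators report SAEs to the Overall PI once the first dose has been given. Section 7.5 reads: "Serious adverse events will be recorded from the time treatment", and words seem to be missing at that point. Section 7.10.1 requires reports to the Overall PI of "any serious adverse event (SAE) that occurs after informed consent, during treatment, or within 90 days of the last dose". Section 7.2 defines a class of adverse events that begin after consent but before investigational product. Table 7 marks adverse event evaluation in the Pre-Study column. Section 7.13 sends all adverse events, including those reported by expedited routes, to the routine toxicity forms.

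**Analysis.** Section 13.3 describes the toxicity analysis as one "which will include all patients who received study drug regardless of eligibility". Section 13.4.1 adds: "All participants will be evaluable for toxicity from the time of their first dose of study medication".

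**Patients never dosed.** Section 4.1 begins "If a participant does not receive protocol therapy following registration" and goes on to require that the registration be cancelled in OnCore.

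**The concern.** The baseline biopsy is done for the trial's exploratory aims, in patients whose disease, as section 2.1 describes it, often brings lung encasement, hypoxemia and shortness of breath. The trial should be able to say how often that procedure caused harm. As written, it may not be able to.

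Two separate gaps are involved. The first is collection: a site that follows 7.8 would not report a serious complication before the first dose, while a site that follows 7.10.1 would. The second is analysis: even when such an event is reported, 13.3 and 13.4.1 leave it out, and no other summary is planned. The attribution scale in 7.3 adds to this, because it grades relatedness only to study treatment. A complication of the biopsy has no category of its own and would presumably be filed as unrelated.

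What is at stake is a reliable count of baseline-procedure complications, for the final report and for the monitoring committee, which reviews toxicity data under 12.2. Response, survival and drug toxicity results are not affected.

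**Working it through.** The plan states no figure on this point, so the check is a comparison of sections, followed by one illustration.

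**Step 1. Start points side by side**

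| Section | What it governs | Start point | Covers the baseline biopsy? |
|---|---|---|---|
| 7.8 | SAE reports to the Overall PI | Initial dose | No |
| 7.5 | AE and SAE collection | Apparently treatment (text damaged) | Apparently no |
| 7.10.1 | SAE reports to the Overall PI | Informed consent | Yes, serious events only |
| 7.2 | Definition of non-treatment-emergent AE | Consent | Yes, as a definition |
| Table 7 | AE evaluation schedule | Pre-Study | Yes, by the mark in that column |
| 7.13 | Routine AE submission | None stated | Not excluded |
| 13.3, 13.4.1 | Toxicity analysis | First dose, dosed patients | No |

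Sections 7.8 and 7.10.1 name the same reporter, the same recipient and the same kind of event, with different start points. Both texts are intact, so the conflict does not depend on 7.5.

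**Step 2. Follow a pre-dose biopsy complication through these rules**

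- *Serious, patient later dosed.* Not reported under 7.8. Reported under 7.10.1 and then carried into routine data by 7.13. Outside the toxicity analysis, because onset precedes the first dose.
- *Serious, patient never dosed.* The same conflict on reporting. Outside the toxicity analysis, because no study drug was received. The primary and secondary analyses in 13.3 also require that therapy was started.
- *Not serious, dosed or not.* 7.10.1 does not apply. Collection rests on the Table 7 mark, 7.2 and the general wording of 7.13, against the apparent treatment start in 7.5. Outside the toxicity analysis.

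**Step 3. Limit the scope**

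The second biopsy is different. Section 9.1.2 says: "The on-treatment biopsy may be obtained anytime between Cycle 2 Day 1", which is after the first dose, so its complications fall inside the toxicity window. The gap concerns the baseline procedure only.

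**Step 4. Illustration of scale**

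Inputs: n = 40 baseline procedures, taken from the planned sample size in 13.2 as a nominal count; q = probability of a complication per procedure, assumed, since the documents give none. Expected number = n × q. Chance of at least one = 1 − (1 − q)^n.

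| Assumed q | Expected events | Chance of at least one |
|---|---|---|
| 1% | 40 × 0.01 = 0.4 | 1 − 0.99^40 = 0.331 |
| 2% | 40 × 0.02 = 0.8 | 1 − 0.98^40 = 0.554 |
| 3% | 40 × 0.03 = 1.2 | 1 − 0.97^40 = 0.704 |
| 5% | 40 × 0.05 = 2.0 | 1 − 0.95^40 = 0.871 |
| 10% | 40 × 0.10 = 4.0 | 1 − 0.90^40 = 0.985 |

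The true number of procedures could be below 40 because of the feasibility exceptions, or above it if some patients are biopsied and never start therapy.

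**The case against.** The strongest reply is that the plan already handles most of this. Section 7.10.1 obliges investigators to report serious events from consent, 7.13 puts events reported by expedited routes into the routine data, Table 7 schedules a Pre-Study adverse event evaluation, and 7.2 names the class of event. A reader might infer from 13.4.1 that biopsy harms stay out of the safety data altogether. These sections do not support that: at least serious pre-dose events have a route into the records, and the Cycle 2 biopsy is inside the toxicity window.

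A reader might also infer from 4.1 that a patient harmed by the biopsy and never dosed disappears from the dataset. Section 4.1 cancels a registration. It does not delete adverse event records or waive 7.10.1. The biopsy is timed from consent rather than from registration, so 4.1 may not even come into play.

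Third, 13.3 and 13.4.1 are not errors. The secondary objective is the safety of the drug combination, and a set of treated patients followed from the first dose is the standard choice for that. An event before exposure cannot be drug toxicity. A biopsy complication that worsens after dosing could still be counted, since 7.2 treats clinically significant worsening of an existing condition as an adverse event.

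Fourth, 7.5 is visibly damaged where the start point should be, possibly by text extraction, and 7.8 is headed as reporting to the drug supplier.

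All of this stands, and it narrows the point. It does not remove the conflict: the opening sentence of 7.8, whatever its heading, addresses reports to the Overall PI, as 7.10.1 does. Nor does it supply a planned summary of pre-dose procedure events or settle collection of non-serious ones.

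**Conclusion.** The point holds in a limited form. The protocol contradicts itself on when SAE reporting to the Overall PI begins: initial dose in 7.8, informed consent in 7.10.1. Section 7.5 apparently agrees with 7.8; 7.2 and Table 7 agree with 7.10.1. A mandatory research biopsy, with feasibility exceptions, is taken in the disputed interval. Its complications may therefore be collected inconsistently, and unless they worsen after dosing they enter no planned safety analysis, including for patients never dosed.

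The size cannot be derived from the documents. The 33% to 70% chance of at least one complication is illustration only: it assumes a rate of 1% to 3%, independent procedures and a nominal count of 40. The conclusion rests on the intact text of 7.8, 7.10.1, 9.1.2, 13.3 and 13.4.1, and does not need that figure or the damaged wording of 7.5.

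**What to change.** 1. Reconcile 7.5 and 7.8 with 7.10.1 so that adverse events and SAEs attributed to a study procedure are collected from informed consent. Restore the missing words in 7.5.
2. Record these events for everyone who undergoes the pre-treatment biopsy, including patients never dosed and those whose registration is cancelled under 4.1, and say so there.
3. Add relatedness to a study procedure to the attribution items in 7.3, so that the events can be identified.
4. In section 13, add a descriptive listing of procedure-related events with the number of patients biopsied at baseline as denominator, reported apart from drug toxicity. Leave the first-dose, as-treated set in 13.3 and 13.4.1 as it is.

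The cost is protocol wording, a short pre-dose adverse event form and slightly more data entry. Sample size, the two-stage rule and the efficacy analyses do not change.

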13.4.2 Evaluation of the Primary Efficacy Endpoint

All eligible participants included in the study will be assessed for response, even if there are major protocol therapy deviations. Each participant should be assigned one of the following categories: 1) complete response, 2) partial response, 3) stable disease, 4) progressive disease, 5) early death from malignant disease, 6) early death from toxicity, 7) early death because of other cause, or 9) unknown (not assessable, insufficient data). By arbitrary convention, category 9 usually designates the "unknown" status of any type of data in a clinical database.

APPENDIX A PERFORMANCE STATUS CRITERIA

ECO	OG Performance Status Scale	Karnofsky Performance Scale			
Grade	Descriptions	Percent	Description		
0	Normal activity. Fully active, able to carry on all pre-disease	100	Normal, no complaints, no evidence of disease.		
0	performance without restriction.	90	Able to carry on normal activity; minor signs or symptoms of disease.		
1	Symptoms, but ambulatory. Restricted in physically strenuous activity, but ambulatory and able	80	Normal activity with effort; some signs or symptoms of disease.		
1	to carry out work of a light or sedentary nature (e.g. , light housework, office work).	70	Cares for self, unable to carry on normal activity or to do active work.		
2	In bed <50% of the time. Ambulatory and capable of all self-care, but unable to carry out	60	Requires occasional assistance, but is able to care for most of his/her needs.		
	any work activities. Up and about more than 50% of waking hours.	50	Requires considerable assistance and frequent medical care.		
3	In bed >50% of the time. Capable of only limited self-care, confined	40	Disabled, requires special care and assistance.		
3	to bed or chair more than 50% of waking hours.	30	Severely disabled, hospitalization indicated. Death not imminent.		
4	100% bedridden. Completely disabled. Cannot carry on any	20	Very sick, hospitalization indicated. Death not imminent.		
4	self-care. Totally confined to bed or chair.	10	Moribund, fatal processes progressing rapidly.		
5	Dead.	0	Dead.		

APPENDIX B COCKCROFT-GAULT EQUATION FOR CREATININE CLEARANCE

Males:						
Creatinine (mL/min)	CL	II	Weight (kg) x ( 72 x serum creati		- /	
Females:						
Creatinine (mL/min)	CL	=	Weight (kg) x (140 – Age) 72 x serum creatinine (mg/dL)	x	0.85
